9.3. Statistical Analyses

The SAP will be developed and finalized before any analyses are performed and will describe the analyses and procedures for accounting for missing, unused, and spurious data. This section is a summary of the planned statistical analyses of the primary and CCI [REDACTED] endpoints.

9.3.1. Pharmacokinetic Analyses

9.3.1.1. Derivation of Pharmacokinetic Parameters

Plasma PK parameters for tafamidis will be derived (as data permit) from the concentration-time data using standard noncompartmental methods as outlined in Table 5. Actual PK sampling times will be used in the derivation of PK parameters. In the case that actual PK sampling times are not available, nominal PK sampling time will be used in the derivation of PK parameters.

Table 5. Plasma Tafamidis Pharmacokinetic Parameters Definitions

Parameter	Definition	Method of Determination
AUC _{last}	Area under the concentration-time curve from 0 to time of last measurable concentration	Linear/Log trapezoidal method
AUC _{inf} *	Area under the concentration-time curve from time 0 to infinity	AUC _(0-t_{last}) + (C _{last} */k _{el}), where C _{last} * is the estimated plasma concentration at the last quantifiable time point (C _{last}) estimated from the log-linear regression analysis C _{last} * = C _{last} x e ^(-k_{el} x t_{last})
CCI [REDACTED]	[REDACTED]	[REDACTED]
C _{max}	Maximum observed concentration	Observed directly from data
CCI [REDACTED]	[REDACTED]	[REDACTED]

Table 5. Plasma Tafamidis Pharmacokinetic Parameters Definitions

Parameter	Definition	Method of Determination
CCl	[REDACTED]	[REDACTED]

*if data permit

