2.1. Modifications to the Analysis Plan Described in the Protocol

None.

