3.2. Secondary Endpoint

Not applicable.

CCI

Table 3. Plasma Tafamidis Pharmacokinetic Parameters Definitions

Parameter	Definition	Method of Determination
AUC_{last}	Area under the concentration-time curve from 0 to time of last measurable concentration	Linear/Log trapezoidal method
AUC_{inf}^*	Area under the concentration-time curve from time 0 to infinity	$AUC_{(0-tlast)} + (C_{last}^* / k_{el})$, where C_{last}^* is the estimated plasma concentration at the last quantifiable time point (C_{last}) estimated from the log-linear regression analysis $C_{last}^* = C_{last} \times e^{(-k_{el} \times t_{last})}$
CCI		
C_{max}	Maximum observed concentration	Observed directly from data
CCI		

*if data permit

CCI

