6. ANALYSES AND SUMMARIES

6.1. Primary Endpoints

For assessment of the relative bioavailability objective of the study, natural log transformed AUC_{inf} , AUC_{last} , AUC_{72} and C_{max} will be analyzed separately using a mixed effect model with sequence, period and treatment as fixed effects and participant within sequence as a random effect. Estimates of the adjusted mean differences (Test-Reference) and corresponding 90% confidence intervals will be obtained from the model. The adjusted mean differences and 90% confidence intervals for the differences will be exponentiated to provide estimates of the ratio of adjusted geometric means (Test/Reference) and 90% confidence intervals for the ratios. Treatment A (Variant 12.2 mg tafamidis free acid tablet) will be the Test treatment, while Treatment B (proposed commercial 12.2 mg tafamidis free acid tablet) will be the Reference treatment.

Residuals from the models will be examined for normality and the presence of outliers via visual inspection of plots of residuals vs predicted values and normal probability plots of residuals but these will not be included in the CSR. If there are major deviations from normality or outliers then the effect of these on the conclusions will be investigated through alternative transformations and/or analyses excluding outliers. Justification for any alternative to the planned analysis will be given in the report of the study.

CCI

PFIZER CONFIDENTIAL

Table 4. PK Parameters to be Summarized Descriptively by Treatment

Parameter	Summary Statistics
AUC_{inf} , AUC_{last} , [REDACTED] [REDACTED]	N, arithmetic mean, median, SD, %CV, minimum, maximum, geometric mean and geometric %CV
C_{max}	
F	

For AUC_{inf} , AUC_{last} , and C_{max} , individual participant parameters will be plotted against treatment. Box and whisker plots for AUC_{inf} (if data permits), AUC_{last} , [REDACTED], and C_{max} , will be plotted by treatment.

[REDACTED]
[REDACTED]
[REDACTED]

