Appendix 2. List of Abbreviations

Abbreviation	Term
%CV	coefficient of variation
AE	adverse event
CCI	
AUC _{inf}	area under the concentration-time curve from time 0 to infinity
AUC _{last}	area under the concentration-time curve from 0 to time of last measurable concentration
BLQ	below the limit of quantitation
BP	blood pressure
CaPS	Clinical Data Interchange Standards Consortium and Pfizer Standards
CI	confidence interval
C _{last}	estimated plasma concentration at the last quantifiable time point estimated from the log-linear regression analysis
C _{max}	maximum observed plasma concentration
CSR	clinical study report
ECG	electrocardiogram
HR	heart rate
k _{el}	the terminal phase rate constant calculated by a linear regression of the loglinear concentration-time curve
LLQ	lower limit of quantitation
mg	milligram
N/A	not applicable
NC	not calculated
ND	not done
NS	no sample
PK	pharmacokinetic(s)
PR	pulse rate
QRS	Combination of Q-, R- and S- wave on an electrocardiogram representing ventricular depolarization
QTc	corrected QT
QTcF	corrected QT (Fridericia method)
RR	respiratory rate
SAP	statistical analysis plan
SD	standard deviation
SoA	schedule of activities
CCI	
TEAE	treatment emergent adverse event
t _{last}	time of last measurable concentration
CCI

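### The printed equation for Clast* in Protocol Table 5 and SAP Table 3 contradicts its verbal definition and, if programmed as printed, understates AUCinf

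*Protocol*

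**What the plan says.** AUCinf, where the data allow it, is a primary endpoint alongside Cmax (Protocol Section 3; SAP Sections 2.2 and 3.1). Protocol Section 9.3.1.1, Table 5, defines it as the area up to tlast plus Clast*/kel. The cell describes Clast* in two ways:

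- In words: it "is the estimated plasma concentration at the last quantifiable time point", obtained from the log-linear regression.
- As an equation: Clast* = Clast × e^(−kel × tlast).

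SAP Section 3, Table 3, carries the same two statements; its right-hand side begins "C_{last} \times e^{(-k_{el} \times t_{last" (closing brackets omitted here). SAP Section 2.1, headed "Modifications to the Analysis Plan Described in the Protocol", answers that there are none.

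SAP Appendix 2 describes kel as "the terminal phase rate constant calculated by a linear regression of the loglinear concentration-time curve". It also has an entry labelled Clast, without an asterisk, that reads "estimated plasma concentration at the last quantifiable time point estimated from the log-linear regression analysis".

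The protocol says the parameters come from "standard noncompartmental methods as outlined in Table 5". AUCinf is analysed in the mixed model and summarised by treatment in SAP Section 6.1, Table 4, with "N, arithmetic mean, median, SD, %CV, minimum, maximum, geometric mean and geometric %CV".

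**The concern.** A log-linear terminal regression predicts the concentration at tlast as exp(intercept) × e^(−kel × tlast), starting from the line's value at time zero. The printed equation starts instead from Clast, which is already the concentration at tlast. It therefore returns roughly the concentration expected at 2 × tlast. One cell thus gives two different rules for the extrapolated part of a primary endpoint, and no other visible text says which governs.

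If the equation is followed, each participant's extrapolated area is too small and the reported AUCinf means, medians and geometric means are too low. The share of AUCinf that is extrapolated also looks smaller than it is, which would mislead anyone judging how far AUCinf can be trusted.

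**Working it through.** **Inputs.** The last sampling time is 168 h (Protocol Table 2), taken as tlast. The AUCinf formula and both versions of Clast* come from Protocol Table 5 and SAP Table 3. Neither document visibly states a half-life, so 20, 30, 40, 60 and 80 h are assumed. The profile is an assumed one-compartment oral curve with ka = 1 per h at the 16 nominal times. AUC uses the linear-up/log-down rule, and kel and the intercept come from the last 4 points.

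**The plan's own figure.** The documents give no number for Clast*. The only related figure is the precision table in Protocol Section 9.5. For AUC the log half-width is t(0.95, 10 df) × 0.098 × √(2/12) × √(χ²(0.80, 10 df)/10) = 0.0841. Then 100 × e^(∓0.0841) = 91.94 and 108.77, as printed. This does not depend on the Clast* equation.

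**Step 1, algebra.** Let p be the regression prediction at tlast.

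- Verbal rule: extrapolated area = p/kel.
- Printed equation: extrapolated area = Clast × e^(−kel × tlast)/kel.

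With Clast close to p, the second is the first multiplied by e^(−kel × tlast), which is below 1 whenever kel and tlast are positive. The direction reverses only if the observed Clast exceeds the prediction by more than e^(kel × tlast), which is about 7-fold at a half-life of 60 h.

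**Step 2, size for one profile.** With kel = ln 2 / half-life:

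- factor = e^(−kel × 168)
- true extrapolated share = ka/(ka − kel) × factor
- understatement = share × (1 − factor)

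At 60 h, kel = 0.01155 per h, the factor is 0.1436, the share is 1.0117 × 0.1436 = 14.53%, and the understatement is 14.53% × 0.8564 = 12.44% (12.45% with the trapezoidal AUC).

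| Assumed half-life (h) | Factor on extrapolated area | AUCinf understated by |
|---|---|---|
| 20 | 0.003 | 0.31% |
| 30 | 0.021 | 2.07% |
| 40 | 0.054 | 5.24% |
| 60 | 0.144 | 12.45% |
| 80 | 0.233 | 18.05% |

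At 60 h the true extrapolated share of 14.5% would appear as 2.4%.

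**Step 3, effect on the Test/Reference ratio.**

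- *Same kel and tlast.* With assumed Test F = 0.90 and ka slowed to 0.3 per h, the correct ratio is 0.897 to 0.899 and the printed equation gives 0.895 to 0.897. The shift is 0.03 to 0.43 percentage point.
- *Random kel variation between periods.* With a CV of 5% or 10%, the simulated geometric mean ratio moves by under 0.05 point.
- *One of 12 participants misses only the 168 h sample in one period.* The 12-participant ratio moves by at most 0.3%.
- *Systematically lower kel for Test.* The ratio moves by 0.1% to 1.2% for a 5% difference and 0.2% to 2.4% for a 10% difference. The documents give no reason to expect either.

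**The case against.** The strongest reply is that this is a slip of one symbol. Table 5 holds the words as well as the equation, and only the words describe a standard noncompartmental quantity, so a sensible reader would follow them. If Clast has the meaning given in SAP Appendix 2, the equation is self-referential and cannot be programmed at all; the understatement arises only if Clast is read as the observed value. The study's aim is a ratio, and the shift with equal kel is at most 0.43 point against a planned 90% interval width of 15.15 points at a 90% ratio (0.43/15.15, about 3%). The size for absolute AUCinf rests on assumed half-lives and runs from 0.31% to 18.05%. The missing asterisk in Appendix 2 may simply have been lost when the text was extracted.

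Most of this stands as a limit on the consequences. It does not make the equation right. The reference to standard methods points back to the table containing the contradiction, and the documents do not name the software that would settle the matter. The same equation appears in both documents in different typesetting, so it is unlikely to be an extraction fault. If the equation is not meant to be used, that is a reason to remove it. The Appendix 2 label is a side point and should be checked against the source file.

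**Conclusion.** The concern holds. The equation for Clast* is wrong as printed in both documents and contradicts the definition beside it. The error follows from algebra alone, and its direction does not depend on the half-life.

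Its size does. AUCinf would be 0.31% to 18.05% too low for assumed half-lives of 20 to 80 h with sampling to 168 h, and only if the equation is programmed with the observed Clast. The comparison of the two tablets is nearly untouched unless kel differs systematically between them. AUClast, Cmax and the sample size are unaffected, and with no hypothesis tested no decision would change. It should be fixed because it sits in the definition of a primary endpoint.

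**What to change.** In Protocol Table 5 and SAP Table 3, replace the equation with Clast* = C0* × e^(−kel × tlast), where C0* = exp(intercept) of the same terminal log-linear regression that gives kel. Alternatively, delete the equation and keep the verbal definition. In SAP Appendix 2, make sure the entry for the regression estimate is labelled Clast*, so that it is distinct from the observed Clast.

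The cost is one line in each document and, if needed, one label. Sampling and study conduct do not change.

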9.3.2 Statistical Methods for PK Data

For assessment of the relative bioavailability objective of the study, natural log transformed AUC_{inf} , AUC_{last} , C_{max} and C_{max} will be analyzed separately using a mixed effect model with sequence, period and treatment as fixed effects and participant within sequence as a random effect. Estimates of the adjusted mean differences (Test-Reference) and corresponding 90% confidence intervals will be obtained from the model. The adjusted mean differences and 90% confidence intervals for the differences will be exponentiated to provide estimates of the ratio of adjusted geometric means (Test/Reference) and 90% confidence intervals for the ratios. Treatment A (Variant 12.2 mg tafamidis free acid tablet) will be the Test treatment, while Treatment B (proposed commercial 12.2 mg tafamidis free acid tablet) will be the Reference treatment.

The PK parameters AUC_{inf} , C_{max}, AUC_{last} , C_{max} of tafamidis will be summarized descriptively by treatment. For AUC_{inf} , AUC_{last} , and C_{max}, individual participant parameters will be plotted against treatment. Box and whisker plots for AUC_{inf} (if data permits), AUC_{last} , C_{max}, will be plotted by treatment.

The plasma concentrations for tafamidis will be listed and summarized descriptively by nominal PK sampling time and treatment. Individual participant as well as mean and median profiles of the plasma concentration time data will be plotted by treatment using actual (for individual) and nominal (for mean and median) times respectively. Mean and median profiles will be presented on both linear and semi-log scales.

For summary statistics and median plots by sampling time, the nominal PK sampling time will be used. For individual participant plots by time, the actual PK sampling time will be used.

Additional specifications about the tables, listings, and figures will be outlined in the SAP.

9.3.2. Safety Analyses

All safety analyses will be performed on the safety population.

AEs, ECGs, BP, pulse rate, and safety laboratory data will be reviewed and summarized on an ongoing basis during the study to evaluate the safety of participants. Any clinical laboratory, ECG, BP, and pulse rate abnormalities of potential clinical concern will be described. Safety data will be presented in tabular and/or graphical format and summarized descriptively, where appropriate.

Medical history and physical examination and neurological examination information, as applicable, collected during the course of the study, will be considered source data and will not be required to be reported, unless otherwise noted. However, any untoward findings identified on physical and/or neurological examinations conducted during the active collection period will be captured as AEs, if those findings meet the definition of an AE. Data collected at screening that are used for inclusion/exclusion criteria, such as laboratory data, ECGs, and vital signs, will be considered source data, and will not be required to be reported, unless otherwise noted. Demographic data collected at screening will be reported.

CCI

9.4. Interim Analyses

No interim analysis will be conducted for this study. As this is an open label - study, the sponsor may conduct unblinded reviews of the data during the course of the study for the purpose of safety assessment and/or supporting clinical development.

9.5. Sample Size Determination

A sample size of 12 participants will provide adequate precision to estimate the relative bioavailability of PF-06291826 (tafamidis) variant 12.2 mg tafamidis free acid tablets versus proposed commercial 12.2 mg tafamidis tablets administered under fasted conditions in healthy participants. The following table presents the width of 90% CI for different estimated effects, with 80% coverage probability.

Parameter	Estimated Effect (100*Test/Reference)	90% CI		CI Width
AUC	85%	78.15%	92.46%	14.31%
	90%	82.74%	97.89%	15.15%
	95%	87.34%	103.33%	15.99%
	100%	91.94%	108.77%	16.83%
	105%	96.53%	114.21%	17.68%
	110%	101.13%	119.65%	18.52%
	115%	105.73%	125.09%	19.36%
C _{max}	85%	76.75%	94.14%	17.38%
	90%	81.27%	99.67%	18.41%
	95%	85.78%	105.21%	19.43%
	100%	90.30%	110.75%	20.45%
	105%	94.81%	116.29%	21.48%

Parameter	Estimated Effect (100*Test/Reference)	90% CI		CI Width
	110%	99.32%	121.82%	22.50%
	115%	103.84%	127.36%	23.52%

These estimates are based on the assumption that within participant standard deviations of 0.098 and 0.119 for $\log_e AUC_{inf}$ and $\log_e C_{max}$, respectively, obtained as an average from studies B3461030, B3461044 and B3461095.

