4. STUDY DESIGN

4.1. Overall Design

This study will be a Phase 1, open-label, randomized, 2-way crossover, single dose study to estimate the relative bioavailability of PF-06291826 (tafamidis) variant 12.2 mg tafamidis free acid tablets and proposed commercial 12.2 mg tafamidis tablets administered under fasted conditions in healthy participants.

Screening evaluation will occur within 28 days prior to the first dose in Period 1. Participants will be admitted to the CRU at least 12 hours prior to dosing on Day 1 and will be required to stay in the CRU for 8 days in each period. A total of 12 participants will be enrolled. Participants withdrawn from the study may be replaced. Each period will be separated by a washout of at least 16 days between administration of study drug. On Day 1 of each period, participants will receive a single dose of one of the two tafamidis formulations according to the study schema provided in [Table 3](#). Participants are to be fasted 10 hours prior to dosing and 4 hours post-dosing. For the administration, the drug products will be administrated with 240 mL of water. Medication will be administered at approximately 8:00 AM \pm 2 hours on Day 1 of each period according to a computer-generated randomization schedule.

Participants will be randomized to receive one of the treatment sequences shown in Table 3:

Table 3. B3461102 Treatment Sequence Schema

Sequence	Period 1	Period 2
1 (n = 6)	A	B
2 (n = 6)	B	A

The study medications are listed in Table 4.

Table 4. Description of Tafamidis Treatment

Treatment	Study Medication
A	1 x Variant 12.2 mg tafamidis free acid tablet (Test)
B	1 x Proposed commercial 12.2 mg tafamidis free acid tablet (Reference)

Both variant and proposed commercial 12.2 mg tafamidis free acid tablets will be supplied by Pfizer Worldwide Research and Development.

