9.1. Statistical Hypotheses

There are no statistical hypotheses for this study.

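### Does the 80% coverage label in the sample-size section, or the lack of an attrition allowance, undermine the choice of 12 participants?

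*Protocol*

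**What the plan says.** Protocol section 9.5 states that "A sample size of 12 participants will provide adequate precision" and then gives a table for seven assumed Test/Reference ratios, from 85% to 115%, for AUC and for Cmax. The table is introduced by the sentence "The following table presents the width of 90% CI for different estimated effects, with 80% coverage probability". It rests on "within participant standard deviations of 0.098 and 0.119" on the natural-log scale, for AUCinf and Cmax respectively. At a ratio of 100% it shows 91.94% to 108.77% for AUC (width 16.83%) and 90.30% to 110.75% for Cmax (width 20.45%).

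On numbers, Protocol section 4.1 says "A total of 12 participants will be enrolled. Participants withdrawn from the study may be replaced", with six participants per sequence. SAP section 2.3 says the same.

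On purpose, Protocol section 9.1 says "There are no statistical hypotheses for this study". The planned output is an estimate with an interval: "Estimates of the adjusted mean differences (Test-Reference) and corresponding 90% confidence intervals will be obtained from the model" (Protocol, Statistical Methods for PK Data).

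**The concern.** Two things catch the eye.

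- **The label.** Coverage is the probability that an interval contains the true value. For a 90% interval that is 90%, so the sentence appears to give one interval two coverages. Taken literally, a reader might suspect that the table was computed at the wrong level.
- **The completer condition.** A width for 12 participants in a two-period crossover needs 12 people with usable data in both periods. The plan enrols exactly 12, states no dropout allowance, and makes replacement optional.

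With no hypothesis and no power calculation, this table is the only quantitative support for the sample size. Had it been computed wrongly, or had attrition pushed the precision below a stated requirement, the basis for 12 would be unsound.

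**Working it through.** **Inputs**

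- Within-participant SD 0.098 (AUCinf) and 0.119 (Cmax): Protocol 9.5.
- n1 = n2 = 6: Protocol 4.1, Table 3. Degrees of freedom = 6 + 6 − 2 = 10.
- Two-sided 90% interval: Protocol, Statistical Methods for PK Data, and SAP 6.1.
- The 80% figure: Protocol 9.5.

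**Step 1. Reproduce the table.** On the log scale,

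half-width = SD × √[0.5 × (1/n1 + 1/n2)] × t(0.95, df) × √[χ²(0.80, df)/df].

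The last factor allows for sampling error in the estimated SD. It makes the result the width that the observed interval will not exceed with probability 80%.

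With 6 + 6: √(1/6) = 0.40825, t(0.95, 10) = 1.8125, and √(13.442/10) = 1.1594.

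- AUC: 0.098 × 0.40825 × 1.8125 × 1.1594 = 0.08407. Limits at 100%: 91.94% to 108.77%, width 16.83%.
- Cmax: 0.119 × 0.40825 × 1.8125 × 1.1594 = 0.10209. Limits at 100%: 90.30% to 110.75%, width 20.45%.

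Both match. Multiplying the limits by each assumed ratio gives all 14 rows, with a largest difference of 0.005 percentage points.

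**Step 2. Test the other readings (AUC at 100%).**

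| Reading | Limits | Width |
|---|---|---|
| Protocol table | 91.94 to 108.77 | 16.83 |
| 90% interval with the 80% width factor | 91.94 to 108.77 | 16.83 |
| 90% interval without that factor | 93.01 to 107.52 | 14.52 |
| Literal 80% confidence interval | 94.66 to 105.64 | 10.98 |

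Only the width-probability reading fits. A simulation of 400,000 trials per parameter agrees: the 90% interval covers the true ratio in 90% of trials and is no wider than tabulated in 80%.

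**Step 3. See what fewer completers would do.** The counts below are assumptions. With H the tabulated log half-width and h the half-width without the χ² factor for the reduced numbers, the probability of meeting the tabulated width is P(χ² with df degrees of freedom ≤ df × (H/h)²). For 6 + 5 and AUC, h = 0.07692 and df = 9, so 9 × (0.08407/0.07692)² = 10.75 and P = 0.71. The SD cancels from H/h, so the probabilities are the same for AUC and Cmax.

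| Completers | P(no wider than tabulated) | 80% width at 100%: AUC / Cmax | Width without the factor: AUC / Cmax |
|---|---|---|---|
| 12 (6+6) | 80% | 16.83 / 20.45 | 14.52 / 17.63 |
| 11 (6+5) | 71% | 17.97 / 21.83 | 15.40 / 18.71 |
| 10 (5+5) | 61% | 19.17 / 23.29 | 16.32 / 19.82 |
| 10 (6+4) | 58% | 19.56 / 23.78 | 16.65 / 20.23 |

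The last column is the width obtained if the observed SD equals the assumed one. In every row it stays below the tabulated 16.83 and 20.45. Any information that the mixed model recovers from participants with one period is not counted.

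**The case for a change.** The strongest case for a change is that the only justification of the sample size misnames its key probability. Neither document defines the term, so a reader has to reverse-engineer the table to learn what is claimed. The 80% holds only with 12 participants evaluable in both periods, and "Participants withdrawn from the study may be replaced" permits replacement without requiring it. Data can also be lost without a withdrawal: SAP section 5.3.1 drops known biased parameters, for instance after early vomiting, and sets parameters that could not be calculated to missing. The replacement sentence does not reach those cases. A one-line rewording would cost almost nothing.

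The facts in this stand: the term is not the right one, and the completer condition is unstated. What does not follow is that anything goes wrong. The interval is called a 90% interval in the sentence and in the column heading, so a statistician will attach the 80% to the width. The SAP's model and example code also use 90% intervals, and nothing in the analysis depends on the label. Replacement is the plan's means of handling attrition. The setting is short and controlled: healthy volunteers, two supervised single doses and residence in the unit. Making replacement mandatory would harden an existing discretion without correcting any result.

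**Conclusion.** No change to the plan is needed. The label is a clerical slip over a table that is arithmetically correct. It is also cautious, because it includes an allowance for SD uncertainty that widens the AUC interval at 100% from 14.52 to 16.83 percentage points and the Cmax interval from 17.63 to 20.45.

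The dependence on 12 participants with data in both periods is real but implicit in a precision statement made for 12. Losing one without replacement would lower the stated probability from 80% to 71%; losing two would lower it to 61% (5+5) or 58% (6+4). With 5+5 the 80% limits at a ratio of 100% would still be 90.87% to 110.04% for AUC and 89.03% to 112.32% for Cmax. Neither document states a target width, margin or acceptance limit, so none of these outcomes fails a criterion of the plan.

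This rests on the protocol's SDs holding and on assumed completer counts. A stated precision target would reopen the attrition question; the relabelling would remain editorial.
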